
¹ The Impact of Employee Wellness Programs. NIH ClinicalTrials.gov. U.S. National Library of Medicine. 2017 May 30. (<https://clinicaltrials.gov/ct2/show/NCT03167658>); The Impact of Employee Wellness Programs: A Randomized Controlled Trial. American Economic Association Randomized Controlled Trial Registry. 2015 Feb 3. (<https://www.socialscisearch.org/trials/586/history/26720>)

² Song Z, Baicker K. Effect of a Workplace Wellness Program on Employee Health and Economic Outcomes: A Randomized Clinical Trial. JAMA. 2019 Apr 16;321(15):1491-1501.

³ The Kaiser Family Foundation. Employer Health Benefits: 2019 Annual Survey. 2019. (<https://www.kff.org/health-costs/report/2019-employer-health-benefits-survey/>)

⁴ Jones D, Molitor D, Reif J. What do Workplace Wellness Programs do? Evidence from the Illinois Workplace Wellness Study. Q J Econ. 2019 Nov;134(4):1747-1791.

This second analysis plan details the evaluation of this intervention and specific methodology through the three-year period spanning January 2015 through December 2017. This analysis evaluates the impact of the workplace wellness program on employee health care spending and utilization, health outcomes, employment, and productivity.

This analysis plan seeks to pre-specify the analysis before comparing outcomes for treatment and control groups, in order to minimize issues of data mining and specification searching. To create this document, we examined data on outcomes for the control group and performed limited comparisons of non-outcome variables between the treatment and control groups (such as pre-randomization demographics). However, we have not conducted any analysis of differences in outcomes between the treatment and control groups post-treatment over this three-year window. Institutional review board approval was granted and maintained through Harvard University.

II. Treatment

The treatment was a longitudinal multi-component workplace wellness program designed to improve the health and wellbeing of workers. It took place at BJ's Wholesale Club, the largest warehouse retail corporation in the Eastern U.S. and third largest warehouse retail company in the country, with approximately 25,000 employees serving 9 million members. BJ's operates about 200 worksites or "clubs" from Maine to Florida and has a demographically and socioeconomically diverse workforce across a variety of work settings.

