The key identifying assumption is that the only mechanism through which being employed in a treatment worksite affects outcomes is through the availability of the wellness program. There are two threats to this assumption. First, to the extent that covariates were not balanced at baseline and those covariates affect the outcomes of interest, that imbalance could bias our estimates. We control for observed covariates and apply weights to balance covariates between treatment and control. Despite these adjustments, unobserved covariates might still be imbalanced.

Second, to the extent that the wellness program affected hiring or tenure of employees, their presence in the data set may be endogenously determined. We address the issue of endogenous entry by pre-specifying a subsample of those who were already employed at the time the intervention began. We defined this more restrictive “stable employment” subsample as comprising employees who had worked continuously for 13 weeks prior to the wellness program. This comes at a cost of reducing the overall sample size. Our goal in choosing the definition for this subsample was to balance the costs and benefits, as detailed in Appendix 2.

In this stably employed subsample, however, exit from the firm's workforce is still potentially endogenous. We deal with this concern in two ways. First, we will test balance on exit between treatment worksites vs. from control worksites overall and for subgroups. Indeed, tenure and time worked are among our primary outcomes. To the extent that we observe any unbalanced exit, we will perform a bounding exercise (assuming that those who exited have outcomes working against any observed effects of the intervention).

D. Subgroup analyses

We pre-specified three subgroup analyses. We selected these subgroups based on differences in key outcomes within the control group for those with different baseline characteristics, such as differences in medical spending by age or in reported exercise by sex (**Table 11**).

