We will analyze how the effect of the wellness program varies along 3 pre-specified dimensions: age (less than 40 years or 40 and above), sex (male or female), and employment status (full-time vs. part-time). In our model, these subgroup analyses are implemented using a set of two-way interaction terms and a triple interaction term. Equation 5 below shows these interaction terms in our ITT framework, using the subgroup analysis on age as the representative equation, where $age40_{it}$ is defined as 1 if the individual is age 40 years or older, and 0 otherwise.

$$\begin{aligned}
 Y_{ijt} = & \beta_0 + \beta_1 TREATMENT_{jt} + \beta_2 TIME_WORKED_{ijt} + \beta_3 Age40_{it} \\
 & + \beta_4 TREATMENT_{jt} * TIME_WORKED_{ijt} + \beta_5 TREATMENT_{jt} * Age40_{it} \\
 & + \beta_6 TIME_WORKED_{ijt} * Age40_{it} + \beta_7 TREATMENT_{jt} * TIME_WORKED_{ijt} * Age40_{it} \\
 & + \rho X_{ijt} + \varepsilon_{ijt}
 \end{aligned} \tag{5}$$

In this model, the coefficient on the triple interaction term, β_7 , represents the marginal effect of an additional unit of exposure (as measured by time worked) among employees 40 years or older who were randomized into treatment. For those under age 40, the effect of the wellness program is represented by $\beta_1 + \beta_4 * Exposure$. For those over age 40, the effect of the wellness program is represented by $\beta_1 + \beta_4 * Exposure + \beta_5 + \beta_7 * Exposure$, or $(\beta_1 + \beta_5) + (\beta_4 + \beta_7) * Exposure$. The average effects for each group can be derived by evaluating this at the average level of exposure. We will evaluate whether any differences are statistically significant.

E. Worksite-level analyses

We complement our analyses at the individual level with analyses at the worksite level. Worksite-level data were generated by aggregating values for individuals up to their initial worksite. This aggregation was weighted by the number of hours each employee worked during the treatment period. The estimating equation below captures the framework of the worksite-level analyses.

$$Y_{kt} = \beta_0 + \beta_1 TREATMENT_{kt} + \beta_2 X_{kt} + \varepsilon_{kt} \tag{6}$$

In equation (6), the subscript k denotes a worksite. Analogous to the individual-level analyses, Y_{kt} represents an outcome for worksite k at time t . $TREATMENT_{kt}$ is a binary indicator of

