Full-time salary	4.7	7.0	21.3	11.6	12.1	21.7	11.5	11.4	21.8
Full-time hourly	37.4	44.3	66.6	38.6	52.4	66.8	49.0	53.6	66.4
Part-time hourly	57.9	48.7	12.1	49.8	35.5	11.4	39.5	35.0	11.8
Worker Type (%)									
Sales worker	43.2	45.3	23.2	38.4	39.0	22.3	36.2	39.3	23.3
Non-sales worker	45.9	41.8	52.4	46.4	42.8	52.8	47.4	43.7	51.6
Other worker	10.9	13.0	24.4	15.3	18.2	25.0	16.5	16.9	25.0

Notes: Table lists demographic characteristics for the sample covered by Cigna weighted by months of Cigna coverage. About a third of the total sample has Cigna coverage. Age is defined as age at the mid-point of the treatment period (June 2016). This is different from the balance table where age is defined as of December, 2014 (pre-treatment). Thus the means of age in this table are larger than those in the balance table across all samples.

Table 3: Impact on Employment

	Employee-level			Stably Employed Subsample			Worksite-level		
	Mean Value in Control Group (1)	Reduced Form (Linear) (2)	2SLS (Linear) (3)	Mean Value in Control Group (1)	Reduced Form (Linear) (2)	2SLS (Linear) (3)	Mean Value in Control Group (1)	Reduced Form (Linear) (2)	2SLS (Linear) (3)
Absenteeism (%)	2.23 (2.30) 41,376			3.39 (1.97) 13,000			2.90 (0.35) 135		
Performance Review (% ≤ 3)	46.59 (49.88) 27,150			63.64 (48.11) 12,916			65.94 (12.41) 135		
Tenure [§]	416.69 (399.87) 41,376			786.57 (376.96) 13,000			76.08 (4.35) 135		

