Notes: Table reports the coefficient on TREATMENT from estimating equation (1) by OLS (column 2), and the coefficient on PARTICIPATION from estimating equation (2) by IV (column 3). Standard errors are listed in parentheses. Column 1 reports the mean of each employment outcome in the control group for each sample (with standard deviation in parentheses, followed by the number of observations for each outcome). All regressions will include demographic and employment controls (age, sex, age-sex interactions, race/ethnicity, Cigna coverage status, full-time status, paid hourly status, and job category) and cluster standard errors at the worksite (for employee-level regressions). Employee-level and stably employed subsample control means are weighted by a weight that balances treatment and control on demographic characteristics. Worksite-level control means are not traditionally weighted: individual-level records are collapsed at the worksite-level and weighted by the total number of hours worked at each worksite. For worksite level results on tenure, the outcome was defined as the percent of total days at the worksite during the study period that was worked by employees at the worksite.

§ Tenure was defined as the number of days worked during the treatment period for the employee-level mean and stably employed subsample mean; it was defined as the percent of the entire treatment period worked by employees in the worksite-level mean.

Table 4: Impact on Medical & Pharmaceutical Spending and Utilization

	Employee-level			Stably Employed Subsample			Worksite-level (per 2000 work hours)		
	Mean in Control Group (1)	Reduced Form (Linear) (2)	2SLS (Linear) (3)	Mean in Control Group (1)	Reduced Form (Linear) (2)	2SLS (Linear) (3)	Mean in Control Group (1)	Reduced Form (Linear) (2)	2SLS (Linear) (3)
Medical Spending									
Total Spending	4800.57 (18559.82)			4721.85 (19056.92)			5044.74 (2994.54)		
Medical Utilization									
Number of Office visits	3.90 (4.47)			3.95 (4.33)			4.21 (0.93)		
Number of Hospitalizations	0.09 (0.40)			0.08 (0.36)			0.08 (0.05)		
Number of ER Visits	0.28 (0.75)			0.26 (0.61)			0.27 (0.11)		
Pharmaceutical Spending									
Total Spending	1237.60 (6921.32)			1227.32 (7115.67)			1317.72 (1145.17)		
Pharmaceutical Utilization									
Number of Distinct Medications	5.49 (6.44)			5.91 (6.54)			6.00 (1.30)		
Total Medication Months	11.20 (19.31)			11.41 (19.37)			12.39 (4.38)		
N	7,174			5,779			135		

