Notes: Table reports the coefficient on TREATMENT from estimating equation (1) by OLS (column 2), and the coefficient on PARTICIPATION from estimating equation (2) by IV (column 3). Standard errors are listed in parentheses. Column 1 reports the mean of each outcome in the control group for each sample (with standard deviation in parentheses). All regressions include demographic and employment controls (age, sex, age-sex interactions, race/ethnicity, full-time status, paid hourly status, and job category) and cluster standard errors at the worksite (for employee-level regressions). Employee-level and stably employed subsample control means are weighted by a weight that balances treatment and control on demographic characteristics. Worksite-level control means are not traditionally weighted: individual-level records are collapsed at the worksite-level and weighted by the total number of hours worked at each worksite.

Table 5: Impact on Biometrics

	Employee-level			Stably Employed Subsample		
	Mean in Control Group (1)	Reduced Form (Linear) (2)	2SLS (Linear) (3)	Mean in Control Group (1)	Reduced Form (Linear) (2)	2SLS (Linear) (3)
Cholesterol (mg/dl)	179.87 (38.71) 1,392			184.88 (37.85) 739		
HDL (mg/dl)	49.47 (14.58) 1,366			50.51 (14.87) 720		
Glucose (mg/dl)	104.76 (35.71) 1390			105.79 (38.17) 736		
Systolic BP (mmHg)	124.84 (18.55) 1,400			127.22 (18.73) 738		
BMI	29.79 (7.27) 1,403			30.04 (6.71) 742		

Notes: Table reports the coefficient on TREATMENT from estimating equation (1) by OLS (column 2), and the coefficient on PARTICIPATION from estimating equation (2) by IV (column 3). Standard errors are listed in parentheses. Column 1 reports the mean of each biometric outcome in the control group for each sample (with standard deviation in parentheses, followed by the number of observations for each outcome). All regressions include demographic and employment controls (age, sex, age-sex interactions, race/ethnicity, Cigna coverage status, full-time status, paid hourly status, and job category) and cluster standard errors at the worksite (for employee-level regressions). Control means are weighted by a weight that balances treatment and control on demographic characteristics.

Table 6: Impact on Self-Reported PHA Responses

	Employee-level			Stably Employed Subsample		
	Mean in Control Group (1)	Reduced Form (Linear) (2)	2SLS (Linear) (3)	Mean in Control Group (1)	Reduced Form (Linear) (2)	2SLS (Linear) (3)
Domain 1: Health Behaviors						

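### Tables 3 to 6 test 28 outcomes with no stated alpha, no complete primary-outcome list or hierarchy, and no multiplicity adjustment, so some false positives should be expected at the conventional level

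*Combined protocol and SAP*

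**What the plan says.** The introduction says the analysis is specified before outcomes are compared between arms, "in order to minimize issues of data mining and specification searching". The outcomes are set out in four table shells:

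- "Table 3: Impact on Employment": 3 outcomes
- "Table 4: Impact on Medical & Pharmaceutical Spending and Utilization": 7 outcomes
- "Table 5: Impact on Biometrics": 5 outcomes
- "Table 6: Impact on Self-Reported PHA Responses": 13 outcomes, of which 8 fall under "Domain 1: Health Behaviors" and 5 under a second domain, health and well-being

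Every outcome has columns for the full sample and for the stably employed subsample. The 10 outcomes in Tables 3 and 4 also have worksite-level columns. Section VI.A adds that the main-effect and exposure-interaction coefficients will be shown in parallel tables.

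On priority among outcomes, Section VI.C contains one remark: "Indeed, tenure and time worked are among our primary outcomes". The list is not completed anywhere. Time worked has no row of its own in Tables 3 to 6; it is the exposure variable in equation (1).

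Significance is used in two places. For the three subgroup dimensions (age, sex, full-time or part-time), Section VI.D says "We will evaluate whether any differences are statistically significant". In Section VI.E, worksite-level LATE estimates are produced for those effects that are significant at the individual level. No alpha, adjusted p-value, testing order or summary index appears in the text available for review.

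**The concern.** Pre-specification fixes which tests are run. It does not limit how often at least one of 28 tests crosses a threshold by chance. No outcome is given clear priority, so nothing in the plan tells a reader which significant result to weigh most, or how to read an isolated one.

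The background section makes this matter more. It reports that phase 1 found no significant effects on spending or objective health measures but did find significant effects on self-reported behaviors. The self-reported outcomes are the largest group here, 13 of 28. If one of them is significant in phase 2, a reader with unadjusted p-values alone cannot easily tell a repeat of the phase 1 pattern from a chance finding.

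**Working it through.** The plan gives no alpha, power or family-wise error rate, so there is no figure of its own to reproduce.

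**Inputs**

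- Number of tests: rows of Tables 3 to 6, 3 + 7 + 5 + 13 = 28, counting one full-sample average ITT effect per outcome.
- Alpha: not stated. Two-sided 0.05 per test is assumed; 0.01 and 0.10 are shown as a range.
- Correlation between test statistics: not stated. A range is shown.
- All calculations suppose that the program has no effect on any outcome.

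**Independent tests**

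- At least one false positive: 1 − 0.95^28 = 1 − 0.238 = 0.762.
- Expected number: 28 × 0.05 = 1.4.
- Two or more: 1 − 0.95^28 − 28 × 0.05 × 0.95^27 = 0.41.
- At alpha 0.01: 1 − 0.99^28 = 0.245. At alpha 0.10: 1 − 0.90^28 = 0.948.

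**By table, alpha 0.05, independent**

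| Table | Outcomes | At least one false positive | Expected number |
|---|---|---|---|
| 3 | 3 | 1 − 0.95^3 = 0.14 | 0.15 |
| 4 | 7 | 1 − 0.95^7 = 0.30 | 0.35 |
| 5 | 5 | 1 − 0.95^5 = 0.23 | 0.25 |
| 6 | 13 | 1 − 0.95^13 = 0.49 | 0.65 |

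**Correlated tests, alpha 0.05**

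For m normal statistics with common correlation ρ and critical value c = 1.96, let F(m, ρ) be the chance of at least one false positive:

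F(m, ρ) = 1 − ∫ [Φ((c − √ρ t)/√(1−ρ)) − Φ((−c − √ρ t)/√(1−ρ))]^m φ(t) dt

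With correlation inside families and independence between them, the overall chance is 1 − ∏(1 − F(m_k, ρ)). Four families are the four tables (3, 7, 5, 13). Five families split Table 6 into its two domains (3, 7, 5, 8, 5).

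| ρ | Within four families | Within five families | Common to all 28 |
|---|---|---|---|
| 0.1 | 0.76 | 0.76 | 0.74 |
| 0.3 | 0.71 | 0.72 | 0.64 |
| 0.4 | 0.68 | 0.70 | 0.57 |
| 0.5 | 0.63 | 0.66 | 0.49 |
| 0.7 | 0.53 | 0.57 | 0.33 |
| 0.8 | 0.46 | 0.51 | 0.25 |

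The chance therefore stays above one half up to a within-family correlation of about 0.7 (four families) or 0.8 (five families). With a single correlation across all 28 outcomes, it does so only to just under 0.5.

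**What adjustment within families would leave**

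If each of five independent families is held at 5%, the chance of at least one false positive across all of them is 1 − 0.95^5 = 0.226.

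**The case against.** The best defense is that the outcomes were fixed before arms were compared and all appear in published table shells, so readers can see how many tests were run and discount accordingly. The plan also has no rule that one significant result establishes an effect. The Section VI.E trigger is modest: it produces worksite-level instrumental-variable versions of effects already tested, and Tables 3 and 4 have columns for such estimates anyway. All of this stands and limits the severity. But visibility leaves the correction to the reader, and the plan itself relies on significance without saying at what level.

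Four stronger readings are tempting and should not be drawn.

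- *The plan names no primary outcome.* Section VI.C does place tenure and time worked among the primary outcomes. The defect is that the list is open-ended and unranked.
- *One or two chance findings are to be expected in Table 6.* The expectation there is 13 × 0.05 = 0.65, and under independence the most likely count is zero (0.95^13 = 0.51). The figure of 1.4 belongs to all 28 outcomes.
- *Phase 1 was significant only for self-reported behaviors.* The background section says nothing about phase 1 employment results.
- *The error rate is near certainty, because samples, worksite-level tests and subgroups multiply the count.* Treating 28 + 28 + 10 = 66 estimates as independent gives 0.97, but the samples overlap and the same outcomes recur, so that is not an actual error rate.

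The sentence quoted from Section VI.D concerns subgroup differences, whereas the calculation concerns the main ITT comparisons. It shows that significance is used, not which 28 tests are counted.

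**Conclusion.** The concern holds as a gap in error control. At an assumed two-sided 0.05, the 28 full-sample ITT tests carry a 76% chance of at least one false positive if independent, and about 68 to 70% at an assumed within-family correlation of 0.4. Over within-family correlations from 0.1 to 0.8 the figure runs from about 76% down to 46 to 51%. Strong correlation across all outcomes would lower it further, and at alpha 0.01 with independence it is about 25%. So more likely than not is a fair description only at the conventional level and with weak to moderate correlation.

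The absence of an alpha, a hierarchy and an adjustment is judged on the text supplied. Front matter was removed from that copy, and the trial registrations cited in the first footnote were not available. The plan should be amended on this point, but the gap does not invalidate the design.

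**What to change.** 1. State the significance level and sidedness, and complete the list of primary outcomes that Section VI.C begins.
2. For the main ITT estimates in the full sample, report family-wise adjusted p-values beside the unadjusted ones within five families: Table 3 (3), Table 4 (7), Table 5 (5), Table 6 Domain 1 (8) and Table 6 Domain 2 (5). Westfall-Young step-down with whole worksites resampled or permuted is one suitable method. It respects the clustering and uses the correlation between outcomes, so it is less conservative than Bonferroni.
3. Say that isolated unadjusted results will be interpreted in light of the adjusted values.
4. Apply the same adjustment separately to the stably employed sample as a robustness check.
5. Label the subgroup contrasts exploratory.
6. State that control is within family, which leaves about 23% across five independent families.

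No new data are needed. The introduction says post-treatment outcome differences between arms over the three-year window had not been analyzed when the plan was written; families fixed at that stage would not be informed by results. The cost is some computing, and fewer single outcomes will reach significance.

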randomization into treatment or control, with β_1 indicating the average worksite-level effect of being randomized into treatment. The vector of covariates X_{kt} comprises the same set of observable characteristics for individuals, aggregated to the worksite level using weighted averages (generating percentages for binary variables). The worksite-level regressions are weighted by worksite size, as measured by the total hours worked by all employees at a worksite, with standard errors adjusted for heteroscedasticity. For estimates of program effect that are significant in the individual-level analysis, we will produce parallel LATE estimates at the workplace level, analogously using treatment status as an instrument for participation.

Although the employees at each worksite could change over time, the worksites themselves were all stably represented in our data. However, at the 18-month mark, 5 worksites previously in the control group entered the treatment group. In our base specification, we will assess effects for the 20 worksites that were continuously treated throughout the 3-year period (omitting the additional 5 from the analysis altogether). As an alternative specification, we will also evaluate effects at the worksite level when considering the 5 additional worksites in the treatment group.

F. Sensitivity analyses

We conduct several types of sensitivity analyses. First, in the statistical analyses above, our base regression models use linear regression even for binary outcomes. The OLS estimator has been shown to perform better than other non-linear approaches in estimating the average population effect, particularly with large samples.¹⁰ However, OLS also has limitations, such as its sensitivity to outliers. To test the robustness of our main results to changes in functional form, we will fit logit models for binary outcome variables.

Second, we will present LATE results with alternative definitions of participation. As defined above, these include a binary indicator of participation based on completing at least one module, and a high participation indicator defined as completing at least 3 modules.

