Notes: The average participation rate for each module was calculated as the percentage of individuals who completed a module out of all who were eligible to complete a module during the time that the module was running. Participation is equivalent to completion of a module, with an incentive of a gift card for completion of the module. Descriptions of each module and their criteria for completion are provided in Appendix 1. Employees could only participate in the Take Charge of Your Health module once, though it was run twice. Club Cardio Challenge had two rounds and completion of either round 1 or round 2 earned a gift card; completion of both rounds did not earn an additional gift card, but rather an entry into a raffle for a Fitbit, unless the employee had Cigna health insurance, in which case they could complete both rounds of Club Cardio Challenge for an additional fitness reimbursement. Nutrition for a Lifetime occurred in two rounds; individuals who completed round 1 earned an ActivBAND or gift card. Completion of round 1 and round 2 earned an additional gift card or weight management reimbursement for Cigna members. Values were weighted by the number of days an individual was working during a given module's timeframe.

Panel B. Intensity of Participation by Definition

Definition of Participation	Employees at Treatment Worksites (N = 7288)	Participants at Treatment Worksites (N = 2071)
Completed any module (%)	28.4	100.0
Modules completed (#)	1.17	4.11
3 or more modules (%)	16.7	58.8

Notes: These summary statistics show the intensity of participation in the treatment group according to the 3 definitions of participation. In contrast to Panel A above, the sample (denominator) for these calculations was all employees at treatment worksites (first column) and all employees at treatment worksites who completed any module (second column) throughout the study period. Because of this difference in the denominators, participation rates for a given module in Panel A could exceed the average participation study-wide in Panel B.

Table 8: Balance Between Treatment and Control—Employee Level**Panel A.1: All Employees – Unweighted**

	(1)	(2)	(3)	(4)	(5)
	Treatment (n=7288)	Primary Control (n=7377)	Primary + Secondary Control (n=41376)	(1) vs (2) P value	(1) vs (3) P value
Demographics					
Age (yrs)	33.5	32.8	33.0	0.333	0.358
Female (%)	46.9	46.8	45.6	0.942	0.444
Race (%)				<0.001	<0.001
Black	21.1	25.2	26.7		
White	57.7	51.6	48.8		

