Note: Control means and first stage estimates of the impact of TREATMENT on alternate definitions of PARTICIPATION. All regressions include demographic and employment controls (age, sex, age-sex interactions, race/ethnicity, full-time status, paid hourly status, and job category) and cluster standard errors at the worksite level. All samples other than the sample with Cigna coverage also include a control for whether or not the employee ever had Cigna coverage during the treatment period. Employee-level regressions are weighted by a weight that balances treatment and control on demographic characteristics. Standard errors shown in parenthesis and p-values in brackets.

Panel B: Employee-level—Stably Employed Sub-sample

	All		Surveyed		Cigna	
	(7) Control Mean	(8) Estimated First Stage	(9) Control Mean	(10) Estimated First Stage	(11) Control Means	(12) Estimated First Stage
Completed any module (%)	0.57	49.75 (2.82) [0.00]	3.90	79.22 (2.74) [0.00]	0.97	59.54 (3.24) [0.00]
Modules completed (#)	0.02	2.56 (0.21) [0.00]	0.15	5.41 (0.39) [0.00]	0.04	3.41 (0.29) [0.00]
3 or more modules (%)	0.35	35.04 (2.47) [0.00]	2.96	67.78 (3.39) [0.00]	0.61	45.79 (3.15) [0.00]
Average total incentive payment (\$)	0.75	97.62 (8.45) [0.00]	5.92	217.91 (15.74) [0.00]	1.54	163.36 (13.80) [0.00]
N	13,000	15,344	747	1,396	5,779	6,907

Note: Control means and first stage estimates of the impact of TREATMENT on alternate definitions of PARTICIPATION. All regressions include demographic and employment controls (age, sex, age-sex interactions, race/ethnicity, full-time status, paid hourly status, and job category) and cluster standard errors at the worksite level. All samples other than the sample with Cigna coverage also include a control for whether or not the employee ever had Cigna coverage during the treatment period. Employee-level regressions are weighted by a weight that balances treatment and control on demographic characteristics. Standard errors shown in parentheses and p-values in brackets.

Panel C: Worksite level

	All		Surveyed		Cigna	
	(1) Control Mean	(2) Estimated First Stage	(3) Control Mean	(4) Estimated First Stage	(5) Control Means	(6) Estimated First Stage
Completed any module (%)	0.22	28.19 (1.27) [0.00]	3.07	62.25 (1.89) [0.00]	0.91	57.29 (2.83) [0.00]
Modules completed (#)	0.01	1.17 (0.09) [0.00]	0.11	3.49 (0.22) [0.00]	0.03	3.18 (0.27) [0.00]
3 or more modules (%)	0.12	16.69 (1.12) [0.00]	2.27	46.65 (2.16) [0.00]	0.54	43.68 (2.76) [0.00]

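### Table 10 Panel C appears to collapse participation to worksites by headcount, while Section VI.E weights worksite values by employee hours; a worksite LATE combining the two would be too large, chiefly for the Table 3 outcomes

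*Combined protocol and SAP*

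**What the plan says.** Section VI.E uses two separate weights. Within a site, individual values are combined by employee hours: "This aggregation was weighted by the number of hours each employee worked during the treatment period". Between sites, "The worksite-level regressions are weighted by worksite size, as measured by the total hours worked by all employees at a worksite". The note to Table 9 repeats the within-site rule. The note to Table 10 Panel C names only the between-site weight.

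On the instrumental-variable analysis, VI.E says: "For estimates of program effect that are significant in the individual-level analysis, we will produce parallel LATE estimates at the workplace level", with treatment status as the instrument. On the sample, the base specification is that "we will assess effects for the 20 worksites that were continuously treated throughout the 3-year period". The version with the five added sites is the stated alternative.

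Table 7 Panel B reports participation over all 7,288 employees at treatment sites and mentions no hours weight. Section IV.A2 adds that continuous claims outcomes are shown per 2,000 work hours at worksite level, except distinct medications, which is an hours-weighted average.

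**The concern.** With one instrument and one participation variable, the worksite LATE is the reduced-form effect divided by the first stage. The two parts should describe the same weighted workforce. Employees who stay longer contribute more hours and have more modules open to them, so a headcount participation rate is lower than an hours-weighted one. Dividing an hours-weighted outcome effect by a headcount first stage uses too small a denominator, and the estimated effect per module, or per participant, comes out too large in absolute size. Modules completed is the plan's primary definition of participation, so the matter reaches the main LATE scale.

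**Working it through.** **1. Reproduce Panel C from headcount rates (All column).**

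| Measure | Panel C control mean + first stage | Table 7 Panel B |
|---|---|---|
| Any module (%) | 0.22 + 28.19 = 28.41 | 28.4 |
| Modules completed | 0.01 + 1.17 = 1.18 | 1.17 |
| 3 or more (%) | 0.12 + 16.69 = 16.81 | 16.7 |

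All three agree within 1%. The Panel C control means (0.22, 0.01, 0.12) are also almost the employee-level ones in Panel A (0.21, 0.01, 0.12).

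**2. Other worksite values do move.** Treated-arm age is 33.5 in Table 8 Panel A.1 (unweighted) and 38.5 in Table 9. Control absenteeism in Table 3 is 2.23 at employee level and 2.90 at worksite level.

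**3. Participation by stratum, treated arm.** The stably employed number 2,344 of 7,288 (32.2%; Table 8). Their rates are control mean plus first stage from Table 10 Panel B: 0.57 + 49.75 = 50.32%; 0.02 + 2.56 = 2.58 modules; 0.35 + 35.04 = 35.39%. For the other 4,944 employees, (overall × 7,288 − stable × 2,344) / 4,944 gives:
- any module: (28.4 × 7,288 − 50.32 × 2,344) / 4,944 = 18.0%
- modules: 0.50
- three or more: 7.8%

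**4. Stable share of working time.** Control tenure (Table 3), with days standing in for hours: 13,000 × 786.57 / (41,376 × 416.69) = 0.593.

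**5. Time-weighted first stage.** Treated any-module rate: 0.593 × 50.32 + 0.407 × 18.0 = 37.2%. The control mean, built the same way from Panels A and B, is 0.36%, so the first stage is 36.8. The ratio to Panel C is 36.8 / 28.19 = 1.31. Likewise:
- modules: 1.72 / 1.17 = 1.47
- three or more: 24.0 / 16.69 = 1.44

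The control means are a check free of covariate adjustment. Time weighting predicts 0.36% (any) and 0.21% (three or more), whereas Panel C prints 0.22 and 0.12.

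**6. Sensitivity of the factor, all-employee sample.**
- Treated headcounts with control tenure give a time share of 0.601, which leaves the factors almost unchanged (1.32, 1.49, 1.45).
- Absenteeism outside the stable group is (41,376 × 2.23 − 13,000 × 3.39) / 28,376 = 1.70. The share that reproduces the worksite value is (2.90 − 1.70) / (3.39 − 1.70) = 0.71. The factors are then 1.44, 1.68 and 1.63.
- Modules only: the Table 7 Panel A rates sum to 3.425 over twelve modules and 1.158 over the last four. Assuming the five late sites were offered only those four, the average is (20 × 3.425 + 5 × 1.158) / 25 = 2.97. Multiplied by headcount tenure of 38.0% (416.69 / 1,096 days) this is 1.13, close to 1.17. Multiplied by the worksite tenure of 76.08% it is 2.26, a factor near 1.9.

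**7. Cigna sample (Table 4 outcomes).** From the N rows of Table 10, treated stable staff are (6,907 − 5,779) / (8,559 − 7,174) = 1,128 / 1,385 = 81%. Even with all weight moved to them, the treated levels relative to Panel C are:
- any: 60.51 / 58.20 = 1.04
- modules: 3.45 / 3.21 = 1.07
- three or more: 46.40 / 44.22 = 1.05

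**The case against.** The strongest reply is about scope and consequence. No worksite LATE is reported yet, one is promised only where the individual-level effect is significant, and 2SLS fits its own first stage on its own sample. Nothing says that the printed Panel C coefficients will serve as divisors. Worksite outcomes are not all built by one rule either: claims outcomes are per 2,000 hours and tenure is a percentage of days. The size rests on proxies, on two strata, and on adjusted coefficients combined with raw headcounts. The worksite analysis is complementary, and its ITT estimates are untouched.

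All of this stands as a limit on the point. It does not explain why participation alone fails to shift when other worksite values do. Covariate adjustment is an unlikely explanation, since the control means show the same pattern.

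Three stronger readings are tempting and not supported:
- A reader might infer that every worksite LATE is inflated 1.3 to 1.5 times. Only Tables 3 and 4 have worksite columns, and the Table 4 outcomes use the Cigna sample, where the stratum calculation moves the first stage very little. Hours differences within strata could add to that, but the documents do not quantify them.
- A reader might take N = 160 in Panel C as an error. It is 135 control plus 25 treated sites, which is the pre-specified alternative; it is simply not the base-specification first stage.
- A reader might infer a miscalculated figure. No printed sum is wrong. The issue is a within-site weight that is unstated and appears to differ from the plan's rule.

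**Conclusion.** The All column of Table 10 Panel C appears to be a headcount collapse, at odds with the hours-weighted aggregation in VI.E. The consequence is conditional: it arises if the worksite 2SLS uses this participation variable with hours-weighted outcomes. In that case, LATEs for the Table 3 employment outcomes would be too large in absolute size by roughly 1.3 (any module) to 1.5 (modules completed). This assumes that days approximate hours and that control tenure approximates treated tenure. The two further checks, on assumptions of their own, give 1.4 to 1.7, and near 1.9 for modules, so the range is more likely low than high. For the Table 4 outcomes the figure is only about 1.04 to 1.07. Whether the base LATE would in fact use headcount participation cannot be read from the documents.

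**What to change.** State in VI.E and in the Table 10 note which within-site weight applies to participation. Rebuild the Panel C participation variables with the same employee-hours weights used for outcomes and covariates, and use those variables in the worksite 2SLS. Show the first stage for the base sample, which omits the five late-treated sites (160 − 5 = 155 sites: 20 treated and 135 control), and keep the 25-site panel as the pre-specified alternative. If the headcount collapse was deliberate, say so and justify using different weights in the numerator and denominator of the LATE. The cost is a re-run of one table panel with no new data, and it can be done before any treatment–control comparison of outcomes.
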